2.1.5 Assessments for Target Engagement and Potential Clinical Applicability

We will record self-report ratings of psychotic symptoms (hallucinations and delusions) prior to sonication, during sonication, and post-sonication. In addition we will perform fMRI at baseline and within 10 minutes after completion of sonication to examine effects on Gpi functional connectivity. We will use the same methods that we used in examining Gpi functional connectivity in medication-free schizophrenia patients before and after treatment ⁴⁰. As described above, Cain et al ³⁹ observed hemodynamic changes during sonication and during imaging performed 30 minutes after sonication. Importantly, Folloni and colleagues ¹⁴ targeted the amygdala and the anterior cingulate cortex with a single 40 second train of PLIFUS in macaques and found decreased functional connectivity measured by fMRI 30-110 minutes after sonication with no adverse behavioral or histologic effects. We will utilize a sham-controlled, random-order crossover design, because expectancy may influence our measures, and intra-subject comparisons are far more precise than inter-subject comparisons given the heterogeneity of the illness.

2.2 Name and Description of the Investigational Agent

A detailed description of the device and its related procedures (photos, diagrams, and maintenance protocols) can be found in the DEVICE MANUAL document included in the IRB protocol packet. The Sonicator-1000 system was developed in-house at the NYU Langone Health Tech4Health Institute. It is a neuro-navigated single-element pulsed focused ultrasound platform. The system non-invasively delivers ultrasound sonifications intracranially that selectively target specific areas of the brain. The device is hardwired to only emit ultrasound power levels that do not yield damaging effects to the brain like tissue heating, cavitation, and blood-brain barrier disruption, in order to

ensure safe preservation of tissue integrity. Extensive research has been conducted to determine non-thermal pulse parameters and acoustic intensity levels to safely transmit PLIFUS through the scalp–skull–meninges media while localizing the low ultrasound energy into the brain for inducing neuromodulation. This has also been validated through preclinical and clinical studies using histological methods. The device acoustic output limits follow FDA ETC regulation standards for diagnostic and therapeutic ultrasound ²⁸. Previous human studies with similar laboratory built custom PLIFUS devices have safely induced temporary neuromodulation in healthy subjects with no adverse effects following a single session of sonication.

This type of device has been implemented in several PLIFUS neuromodulation studies with healthy human and neurological disease based studies. Most systems were fabricated and designed in a university institutional lab. No FDA-approved and commercial neuro-navigated single-element pulsed focused ultrasound device platform is available on the market. The Sonicator-1000 neuronavigation system uses the 3Dslicer OpenIGTLink and Plus Toolkit standard network communication protocol used for image-guided interventions. Plus Toolkit and 3Dslicer interface a stereoscopic optical tracking camera (Polaris Spectra or Vicra, Northern Digital, Inc) used to track in real-time the spatial locations of objects (E.g. FUS transducer, patient's head location, navigation stylus, and ultrasound calibration components) within 0.5 mm.

The device control system uses a 2-channel wave generator and radio frequency amplifier to control the single-element focused ultrasound transducer. Transducers of various focal lengths can be interchanged in the device to achieve sonication at cortical or deep brain targets. A water membrane and ultrasound gel are used to couple the ultrasound device to the head yielding ultrasound transmission into the brain. Velcro straps and head cushion shims are used when needed to aid the connection of the water membrane to the head. The particular focal length used to target the Gpi is approximately 5.5 ± 0.5 cm. Transducers are fabricated in-house at Tech4Health via a "Primary Calibration" procedure. A transducer is spatially calibrated to the neuronavigation software by interrogating the focused ultrasound field with a hydrophone scanning system and then assigning a navigation crosshair reference point to the focal point location (peak acoustic intensity in the FUS beam). A certified hydrophone is used to calibrate the acoustic intensity in these calibrations in coordination with the electrical output power of the control system. Spatial and intensity calibration are verified for each transducer during their use on humans via a "Pre-Session Equipment Check". This process involves measuring the transducer function using a transducer power and verifying the transducer is still spatially calibrated to the neuronavigation system. The pre-session equipment check occurs proceeding all FUS sessions at the location of the FUS session. Calibration procedures are described in detail with images and templates for the "Primary Calibration", and "Pre-Session Equipment Check" log forms can be found in the DEVICE MANUAL.

The device operator will be able to monitor the position and power of the PLIFUS beam using the neuronavigation software and transducer power monitor, respectively. Multiple buttons located on the system controls and within reach of the operator can be used to instantly shutoff of the device and stop sonication. The device includes a user manual, calibration certificates, and device operation logs that will be included with the device at all times. All device subsystems are nested into a portable workstation and can be sealed for transport in a protected concert speaker box on wheels.

Operation of the device platform is closely monitored and the methods follow the latest guidelines set by the "International Transcranial Ultrasonic Stimulation Safety and Standards"^{41, 42}. 1) Ultrasound output is continuously observed by the operator via transducer power monitor, verifying sonication is active. 2) The navigation software displays the location of the FUS beam focus in real-time during sonication exposure. 3) The power output of the device is displayed on the control system screen of the wave generator and radio frequency amplifier. 4) The transducer monitor continuously monitors the electrical power into the FUS transducer to verify predetermined acoustic intensity levels are reached. 5) Device shutoff stop buttons are clearly visible and accessible on the control console. 6) The operation of the device requires completion of a strict Pre-Session Equipment Test.

2.2.1 Preclinical Data

2.2.2 Clinical Data to Date

Transcranial ultrasound has been studied in 704 human subjects in 35 trials, including studies in epilepsy, obsessive compulsive disorder, depression, Alzheimer's disease, Parkinson's disease, and chronic pain patients ⁴³. To our

knowledge, PLIFUS has not been studied in schizophrenia. No serious adverse events have been reported in human studies of PLIFUS; mild and transient side effects were reported in 3.3% of 704 subjects, including headache, neck stiffness, worsening mood, scalp heating, muscle twitches, cognitive effects (attention), itchiness, sleepiness, and anxiety⁴³. In one prior study of sonication of the Gpi in 16 healthy volunteers, no adverse events were reported³⁸.

2.2.3 Dose Rationale

The PLIFUS dose (sonication parameters) was selected based on the study by Cain et al³⁸ in which the Gpi was the target of sonication and produced changes in hemodynamics (MRI BOLD) without adverse effects. This method involves a very brief (10 minute) pulsed sequence that delivers relatively low energy, which is much lower than most previous transcranial studies and follow FDA and ETC regulation standards for diagnostic and therapeutic ultrasound. An $I_{SPTA} = 1.5 \text{ W/cm}^2$ is chosen as a conservative acoustic intensity compared to other FUS single-element device neuromodulation studies, where some studies reached up to $I_{SPTA} = 4.4 \text{ W/cm}^2$ at the brain target yielding no adverse effects¹⁸.

2.3 Rationale

PLIFUS is the first noninvasive technology that allows us to interrogate deep-seated brain circuits that have been implicated in schizophrenia. This study will be an exploratory step to link imaging biomarkers and patient self-report of symptom response to sonication of the right Gpi. We believe that PLIFUS may provide therapeutic benefit for two reasons. First, our previous work found that excessive functional connectivity of the Gpi was associated with psychosis, and that therapeutic response to antipsychotic medication was associated with decreased Gpi functional connectivity, whereas Folloni and colleagues¹⁴ found that a single session of PLIFUS targeting the amygdala and anterior cingulate reduced functional connectivity. Second, the mechanism of action of PLIFUS appears to be an increase of neuronal calcium influx via mechanosensitive calcium channels⁴⁴. Calcium channels have been strongly implicated by genetic studies in schizophrenia⁴⁵; PLIFUS may produce compensatory changes in calcium regulation that correct a key molecular deficit in schizophrenia.

2.4 Potential Risks & Benefits

2.4.1 Known Potential Risks

Risks of PLIFUS:

Because ultrasound has been used extensively for many years as a diagnostic tool in other fields of medicine, FDA safety regulations are well-established and well-validated. Some investigations of brain sonication have exceeded these safety guidelines and have not produced serious adverse effects. Theoretical adverse effects at very high levels of energy, far in excess of what will be used in this trial, include injury to brain tissue (lesions, bleeding, disruption of the blood-brain barrier) due to excessive heating or cavitation. In 704 human subjects who have been studied in 35 trials of transcranial ultrasound, no serious adverse events have been reported. Mild and transient side effects have been reported in 3.3% of subjects, including headache, neck stiffness, worsening mood, scalp heating, muscle twitches, cognitive effects (impaired attention), itchiness, sleepiness and anxiety⁴³. Rates of side effects associated with sham sonication have not been reported. The sonication parameters that will be employed adhere to FDA and ETC regulation standards for diagnostic and therapeutic ultrasound²⁸.

While PLIFUS is associated with only mild and transient side effects in healthy participants, it has not previously been studied in schizophrenia. It is possible that sonication of the Gpi might worsen symptoms of schizophrenia. If this happens, we expect it to be a transient effect, consistent with other behavioral effects. To minimize this risk, we will exclude from study individuals with a history of violence, aggression or suicidal behavior. We will be monitoring the severity of psychotic symptoms during sonication and will stop the procedure if symptoms worsen by more than 50% on AHRS and DESA or if the participant expresses clinically significant psychological distress or suicidal ideation. The study psychiatrist will remain with the participant during sonication and for 1 hour after completion of sonication to assess for worsening of psychosis and suicidality. The study psychiatrist will arrange for appropriate monitoring and further assessment after 1 hour if needed based on clinical judgement.

Risks of MRI:

A total of 7 MRIs will be performed using a Siemens 3T Prisma; one prior to the intervention visits and one preceding

and one immediately after each of the two sonication/sham visits. No investigational hardware or software will be used during acquisition of imaging data. There are no known radiation risks associated with MRI. However, individuals with metal implants, such as surgical clips or pacemakers should not have an MRI. Additionally, given that the MRI takes places in a confined space, and there are loud banging noises associated with the procedure, individuals may feel anxious during the procedures. Earplugs will be offered to subjects in an effort to help reduce the MRI related noise and subjects will be told that the MRI can be stopped at any time at his/her/their request. Some subjects may experience muscle twitches or tingling sensations and/or a slight increase in body temperature during some types of scan activity. These are very unlikely under current MR guidelines. The FDA has determined that the most common injury associated with MRIs were burns to the skin, most commonly caused by devices that conduct electrical energy, such as metallic objects, pulse oximeters, or EKG leads. While skin tattoos may, in theory, be conductive, the first systematic study of risks of tattoos in individuals undergoing MRI scans was recently published in the New England Journal of Medicine and found minimal risk⁴⁶. The investigators studied a sample of 330 patients who had a total of 933 unique tattoos, including both professional and self-applied tattoos, and were imaged using a 3T MRI for a total of 585 imaging sessions. They excluded individuals with greater than 5% of their body surface covered by tattoos, with tattoos larger than 20 cm, or with tattoos on face, neck or genitals due to fear of adverse events. These criteria were arbitrarily determined by the investigators without strong evidence support. In this study, one participant reported a “tingling” sensation and one reported a sensation of warmth—no persistent adverse effects were observed. A more recent MRI safety study found these exclusionary criteria to be too stringent because 182 of the 376 participants with tattoos in their study (48.4%) would have been excluded⁴⁷. They included all participants with tattoos regardless of size or location, including those with tattoos larger than 20cm (n = 60), tattoos on head, neck, or genitals (n = 125), and tattoos covering more than 5% of body surface (n = 28). None of these participants reported any adverse effects of MRI. In addition, the aforementioned study uses 3T MRI similar to our study. On the basis of this evidence, we will allow individuals with tattoos to participate regardless of size and location. Participants with tattoos will be instructed to notify the technician if they experience warmth in the location of a tattoo and the imaging session will be immediately terminated. All participants will be screened for metal objects and tattoos by both the research staff and the technicians at the imaging center to ensure that no unsafe conductive materials are present in or on the patient’s body.

In extremely rare cases, a magnet can lose its magnetism, in which case cooling fluids may be released noisily through escape valves and may collect in gas form in the scan room. The gas is not harmful in itself as long as fresh air is available. In this very remote event, participants will immediately be brought out of the magnet room.

Contrast will not be used during the MRI scans for this study.

Loss of confidentiality regarding psychiatric or medical information is a possible risk for which precautions will be taken. Participants will be assigned a study identification code that will be used for all study documents. All identifiers will be redacted from records from this study. Study documents collected in this study will be kept in a locked cabinet. Only research staff who are directly involved in this study will have access to that file.

Several measures have been taken to protect subjects against risks incurred by participation in this protocol. We will screen out potential subjects with medical vulnerabilities, including epilepsy or unstable medical illness, and will exclude individuals with a history of suicidality. Participants will be closely observed for 1 hour after their sonication/sham sessions and will be re-assessed after 24-48 hours and after one week.

2.4.2 Known Potential Benefits

No known potential benefits are associated with a single administration of PLIFUS in individuals with schizophrenia. Results of this study may lead to the development of a new therapeutic approach for psychotic symptoms that do not respond to currently available treatments.

3 Objectives and Purpose

The overall purpose of this study is to determine feasibility and tolerability of PLIFUS sonication of the right Gpi in individuals with schizophrenia and to determine whether a single session of PLIFUS sonication will decrease Gpi functional connectivity and decrease intensity of hallucinations and delusions compared to sham sonication. This pilot study will allow us to determine whether the proposed target and PLIFUS sonication parameters produce detectable changes in our imaging biomarkers in order to demonstrate target engagement and to determine whether

we can detect a signal suggestive of therapeutic efficacy to justify future therapeutic trials. If a single session of PLIFUS does not produce measurable effects in the first 12 completers with good quality imaging data, we will administer 3 sessions of PLIFUS and of sham, each over 5 days, in 4 additional participants.

3.1 Primary Objective

To evaluate tolerability, safety and evidence of target engagement (functional connectivity and symptom change) of a single session of PLIFUS targeting the right Gpi in individuals with schizophrenia compared to sham.

3.2 Secondary Objectives

If the primary objective is not successful, we will test the hypothesis that 3 sessions of PLIFUS targeting the right Gpi administered over 5 days will produce a decrease in Gpi functional connectivity and a reduction in symptoms compared to sham.

4 Study Design and Endpoints

4.1 Description of Study Design

This is a single-site, phase 2, sham-controlled random-order cross-over pilot trial of PLIFUS targeting the right Gpi in individuals with schizophrenia. Twelve individuals with schizophrenia who report continuous hallucinations or delusions of moderate or greater severity will receive one session of PLIFUS and one session of sham PLIFUS in random order, one week apart. If no effect of PLIFUS is detected on measures of functional connectivity or psychotic symptoms in the first 12 completers with good quality imaging data, the trial will be changed to 3 sessions of PLIFUS or sham administered over 5 days for 4 subsequent participants.

Potential participants will be enrolled at NYU Langone Manhattan, NYU Langone Brooklyn, and Bellevue Hospital. Recruitment-only procedures will occur at Manhattan Psychiatric Center (see section 5.5.3). Following informed consent, potential participants will be screened by a psychiatrist who will assess psychiatric and medical status. A Brief Psychiatric Rating Scale will also be administered to assess inclusionary status. Individuals who meet inclusionary and exclusionary criteria will then have a structural MRI performed at the MRI visit and with each fMRI scan at Intervention Visits 1 and 2 to guide neuronavigation of PLIFUS. The two sessions of PLIFUS/Sham will occur in random order, one week apart. Randomization schedule will be done using Matlab. Participants will first have an fMRI for measurement of right Gpi functional connectivity, preceded and followed by symptom rating scales. PLIFUS/sham will then be administered over 10 minutes, during which symptom ratings will again be recorded. Symptom ratings will be repeated 5, 30, and 60 minutes, 1 day and 7 days post-sonication/sham. fMRI will be repeated starting 10 minutes after sonication/sham. Safety assessments will be completed prior to discharge of participants 1 hour after each sonication/sham session and after 24-48 hours and 7 days.

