Brief Summary	
The primary objectives of this study are to examine the tolerability of pulsed low-intensity focused ultrasound (PLIFUS) and its effects on brain function measured via fMRI functional connectivity and symptom response in individuals with schizophrenia. A neuronavigated single-element piezoelectric device will be utilized to noninvasively deliver transcranial PLIFUS sonication to the right globus pallidus interna, a brain region implicated in schizophrenia. We aim to enroll participants with schizophrenia in a random order, sham-controlled crossover trial of a single session of PLIFUS counterbalanced with a single sham sonication session, one week apart until we reach 12 completers. After the participant provides written informed consent, a medical and psychiatric evaluation will be performed to determine eligibility for inclusion in the study. The next visit will involve a structural MRI to guide neuro-navigation. The first intervention visit will include a 10 minute PLIFUS sonication or sham sonication, preceded and followed by MRI brain scans and an exit medical examination. Psychiatric symptoms will be assessed immediately prior to sonication/sham, during sonication/sham, and 5 minutes, 30 minutes, 60 minutes, 1 day and 7 days after sonication/sham. The second intervention visit will consist of sonication or sham preceded and followed by MRI brain scans, in addition to symptom assessments and post-sonication/sham medical evaluation. Participants will be closely monitored during and after procedures for tolerability and adverse effects, including 1 and 7 day follow-up visits. The goal of this pilot study is to establish feasibility and tolerability and to determine whether the sonication procedure produces effects on the imaging biomarker and on symptoms prior to proceeding to therapeutic trials using repeated administration. If PLIFUS effects on fMRI and symptom ratings are not detected in the first 12 completers with good quality imaging data, the trial will be changed to 3 sessions of PLIFUS or sham administered over 5 days for 4 subsequent participants.

Phase	Phase 2

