Objectives	
1. Assess safety and tolerability of PLIFUS of the right Gpi2. Assess whether PLIFUS of the right Gpi reduces Gpi functional connectivity compared to sham3. Assess whether PLIFUS of the right Gpi reduces psychosis (intensity of hallucinations and delusions) compared to sham.4. Assess whether change in Gpi functional connectivity following PLIFUS correlates with change in psychosis5. If a single session of PLIFUS does not reduce functional connectivity or symptoms in the first 12 completers with good quality imaging data compared to sham, assess whether 3 sessions of PLIFUS administered over 5 days reduces functional connectivity and symptoms in 4 subsequent participants.
Methodology	Double blind, random order, sham-controlled crossover trial of a single session of PLIFUS counterbalanced with a single sham sonication session.
Endpoint	Primary endpoint: Change in Gpi functional connectivity Secondary endpoints: Change in self-report Likert Scale scores of intensity of hallucinations and intensity of delusions
Study Duration	One year
Participant Duration	Three weeks
Duration of IP administration	Sonication will be delivered in a pulse pattern over 10 minutes

Population	12 individuals with schizophrenia, male or female, ages 18-55, with at least moderate, continuous hallucinations or delusions. Participants may be medicated or unmedicated, cannot be suicidal, cannot have a history of violence or suicidal behavior and cannot have unstable medical or neurological illness or active substance use disorder or contraindications to PLIFUS or MRI. We will continue enrollment until we obtain 12 completers with good quality imaging data. If a single session of PLIFUS does not reduce functional connectivity or symptoms in the first 12 completers with good quality imaging data compared to sham, 4 subsequent participants will be enrolled to assess whether 3 sessions of PLIFUS administered over 5 days reduces functional connectivity and symptoms.
Study Sites	Recruitment will occur at NYU Langone Health Manhattan, Brooklyn, and Bellevue Hospital. PLIFUS and neuroimaging will be performed at the NYU SoM research imaging center at [name].

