9.1 Measures to Minimize Bias

9.1.1 Enrollment/Randomization/Masking Procedures

Because this is a cross-over study, the primary concern with randomization imbalance is with an order effect. We will examine this possibility statistically. The sham condition consists of an identical procedure during which the sonication equipment produces an identical noise. We believe this will fully mask the treatment condition but will ask participants after each session which condition they believe they received and will analyze these results to verify the success of our masking.

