
17 Attachments

These documents are relevant to the protocol, but they are not considered part of the protocol. They are stored and modified separately. As such, modifications to these documents do not require protocol amendments.

- Device Manual attached

18 Schedule of Events

Activity	Screening Visit [Day -30 to -1]	MRI Visit [Day -30 to -1]	Intervention 1 [Day 0]	Intervention 2 [Day 7, 6-8]	Follow-up [Day 14, 13 to 15]
Study team procedures					
Consent	X				
Medical History	X				
Physical Exam	X				
Vital Signs	X				
Psychiatric History	X				
Psychiatric diagnosis (SCID)	X				
Demographics	X				
BPRS	X				X
PSYRATS			X	X	
BPAQ	X				
AHRS			X	X	
MoCA	X		X	X	
DESA			X	X	

CGI	X		X	X	
Experimental intervention					
Randomization		X			
PLIFUS or sham			X	X	
Safety Assessments					
SAFTEE & addendum			X	X	X
C-SSRS	X		X	X	X
Medical/psychiatric assessment			X	X	X
Imaging Assessments					
Structural MRI		X	X (pre and post-sonication)	X (pre and post-sonication)	
Resting state fMRI			X (pre and post-sonication)	X (pre and post-sonication)

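### Session order is called counterbalanced, but nothing keeps it balanced among the participants analysed, and the primary model has no period term to absorb the imbalance

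*Combined protocol and SAP*

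**What the plan says.** The Methodology row of the Protocol Summary describes a "Double blind, random order, sham-controlled crossover trial of a single session of PLIFUS counterbalanced with a single sham sonication session". Section 4.1 adds "The two sessions of PLIFUS/Sham will occur in random order, one week apart" and, on method, only "Randomization schedule will be done using Matlab". No section gives a sequence ratio, a block size, a list length, a separate list for the three-session stage, or the order that a replacement should receive.

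The number randomised is open-ended. The Population row says "We will continue enrollment until we obtain 12 completers with good quality imaging data", and section 9 bases the primary analysis on completers. The Schedule of Events (section 18) marks randomisation under the MRI Visit, anywhere from Day -30 to Day -1. Exclusion criterion 13 in section 5.2 (recent alcohol or recreational drugs) can be checked only at the intervention visits themselves.

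Section 9.1.1 recognises the issue: "the primary concern with randomization imbalance is with an order effect. We will examine this possibility statistically". The primary model in section 9 contains baseline, treatment, sequence and a random participant effect. It has no term for visit or period. Section 9 also analyses the first 12 and the later 4 separately, and section 3 indicates that each of those 4 receives a block of PLIFUS and a block of sham.

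**The concern.** In a two-period crossover, equal numbers in each order make a first-versus-second-visit difference cancel out of the treatment contrast. With unequal numbers, part of it stays unless the model has a period term. Sequence is a between-participant factor, so including it does not take a period difference out of a within-participant contrast.

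The endpoint is a change within each visit, so the relevant period difference is one in the pre-to-post change itself. Examples would be a different drift between the two scans, or a different expectancy response, on a participant's second exposure to the procedure.

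What is at stake is the switch rule. Sections 6.1.8 and 7.15 compare an observed effect size with 0.5 and do so without statistical tests. A shift in the estimate therefore feeds straight into the decision to move to three sessions. In the stage with 4 participants, one shared order would make PLIFUS versus sham the same comparison as first versus second block.

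**Working it through.** The plan gives no figure to reproduce: 12 is a feasibility choice (section 9, Sample Size), with no power, SD or dropout rate stated.

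**Inputs from the documents.** 12 analysed in stage 1 and 4 in stage 2, analysed separately; threshold 0.5; model terms as in section 9. **Assumptions.** A 1:1 ratio of orders; the completion rates and loss counts below; a period effect of 0.5 SD for illustration.

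**1. Bias without a period term.** Let τ be the treatment effect and π the visit-2 minus visit-1 difference in change. The PLIFUS-minus-sham difference has mean τ − π when PLIFUS comes first and τ + π when sham comes first. With n1 and n2 participants in those orders, the average is τ + π(n2 − n1)/n. The share of π that enters, in absolute value, is |n1 − n2|/n:
- 7:5: 2/12 = 17%
- 8:4: 4/12 = 33%
- 9:3: 6/12 = 50%
- 3:1: 2/4 = 50%
- 4:0: 4/4 = 100%

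**2. Cost with a period term.** The bias goes. The variance relative to an equal split is (n/4)(1/n1 + 1/n2):
- 8:4: 3 × (1/8 + 1/4) = 1.125
- 9:3: 3 × (1/9 + 1/3) = 1.33
- 3:1: 1 × (1/3 + 1) = 1.33
- 4:0: not estimable

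**3. Splits under simple randomisation (assumed).** Binomial(n, 0.5).
- n = 12: 6:6 22.6%, 7:5 38.7%, 8:4 or worse 38.8%, 9:3 or worse 14.6%.
- n = 4: 2:2 6/16 = 37.5%, 3:1 8/16 = 50%, 4:0 2/16 = 12.5%.

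**4. Splits from a balanced list with losses (assumed), n = 12.**
- 16 randomised 8:8, 4 lost at random: 6:6 C(8,2)²/C(16,4) = 784/1820 = 43.1%; 7:5 896/1820 = 49.2%; 8:4 140/1820 = 7.7%.
- 14 randomised 7:7, 2 lost at random: 6:6 49/91 = 53.8%; 7:5 46.2%.
- Simulation (200,000 runs), blocks of 4, each loss replaced by the next on the list:

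| Completion | 6:6 | 8:4 or worse |
|---|---|---|
| 60% | 35% | 18% |
| 75% | 43% | 10% |
| 85% | 53% | 5% |

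At 75% completion, 9:3 or worse is below 1%.

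**5. Against the threshold.** With π = 0.5 SD of the within-person differences, the observed effect size moves by 0.5 × 1/3 = 0.17 at 8:4, by 0.5 × 1/2 = 0.25 at 9:3 or 3:1, and by 0.50 at 4:0.

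**6. After the fix.** At 6:6 and 2:2 the share in step 1 is 0 and the ratio in step 2 is 1.00.

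**The case against.** The plan's wording points towards balance: order is called counterbalanced and a schedule is to be prepared. A reader might infer that orders are drawn by simple randomisation, so that 8:4 or worse has a 39% chance. The documents do not say so; the method is unstated. Under a blocked list at 75% completion, 7:5 or better occurs in about 90% of runs. Next-in-line replacement is likewise an inference from open-ended enrolment, since the protocol is silent on a replacement's order.

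A reader might also infer that every difference between visits contaminates the contrast. Stable level differences cancel, because each session has its own pre-scan and the endpoint is change; the baseline covariate may absorb more. The documents give no reason to expect a large period difference in change.

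A third tempting inference is that 6 versus 6 participants cannot examine an order effect. For a period effect that is not supported. The two orders' mean differences are τ − π and τ + π, so comparing them estimates 2π. A two-sample t-test on 6 versus 6 has 80% power at a gap of about 1.8 SD, which is π of about 0.9 SD, and about 88% power at π = 1 SD. The check is insensitive to small effects but not empty.

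Early randomisation should not bias who is lost before session 1, because participants, raters and the psychiatrist are blind (sections 6.1.5 and 7.1.1). It disturbs balance only by chance.

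Finally, this is an exploratory pilot, and 4 people give weak evidence even at 2:2.

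These points limit the size of the problem for the 12. They do not supply a balancing rule, a period term or a list for the 4.

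**Conclusion.** The concern stands in a limited form. Nothing in the protocol keeps order balanced among those analysed, and the stated model does not remove the bias that imbalance would bring.

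For the 12 the risk is moderate: some imbalance is likely even from a blocked list, but a split of 8:4 or worse has about a 10% chance under the 75% completion scenario. If it occurred, a period term would deal with it at a 12.5% cost in variance.

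For the 4 the problem is more serious. They are analysed alone, so balance in stage 1 cannot help them. If they are simply randomised, there is a 1 in 8 chance of total confounding that no model can undo. A fresh block of four would avoid this if all four complete. A continuation of the stage-1 list might not, because the four could straddle two blocks.

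The bias shares follow from the design and the stated model terms. The probabilities rest on the assumed allocation method and completion rates, and the shifts in effect size on an assumed 0.5 SD period effect. The change is worth making because it is nearly free and protects the estimate compared with 0.5. It does not show that the trial as run will be badly unbalanced.

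**What to change.** In sections 4.1, 9 and 9.1.1, with a matching edit to section 18:

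1. State a 1:1 ratio with permuted blocks aimed at 6:6 in the first 12, and a separate 2:2 list for the 4 three-session participants.
2. Assign order on Day 0, after eligibility has been re-checked, and move the randomisation mark in the Schedule of Events from the MRI Visit to Intervention 1.
3. Give the replacement for any non-evaluable participant the same order as the person replaced. Only the single role that section 6.1.10 allows to see all allocations should issue it. A substitute operator is barred from other participants' allocations, so should be told only the order for the participant being treated.
4. Add a period (visit) term to the primary model. The order check in section 9.1.1 can stay.

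The cost is a new randomisation list and a few protocol sentences. The list-holder could infer some upcoming allocations but is already unblinded. The period term uses one degree of freedom: for the within-person differences, 11 become 10 in the 12, and 3 become 2 in the 4. In the 4 that is a noticeable loss, so there the 2:2 list matters most.
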